	Direct bilirubin $\leq \text{ULN}$ for subjects with total bilirubin levels $> 1.5 \text{ ULN}$
AST (SGOT) and ALT (SGPT)	$\leq 2.5 \text{ X ULN}$ OR $\leq 5 \text{ X ULN}$ for subjects with liver involvement
Coagulation	
International Normalized Ratio (INR) or Prothrombin Time (PT)	$\leq 1.5 \text{ X ULN}$ unless subject is receiving anticoagulant therapy as long as PT or PTT is within therapeutic range of intended use of anticoagulants

Activated Partial Thromboplastin Time (aPTT)	≤1.5 X ULN unless subject is receiving anticoagulant therapy as long as PT or PTT is within therapeutic range of intended use of anticoagulants, or subject is shown to have an antiphospholipid antibody on workup
^a Creatinine clearance should be calculated per institutional standard.	

9. For women of childbearing potential: agreement to remain abstinent (refrain from heterosexual intercourse) or use contraceptive methods that result in a failure rate of ≤1% per year during the treatment period and for at least 3 months after the last dose mosunetuzumab or 6 months after the last dose of obinutuzumab. Women must refrain from donating eggs during this same period. A woman is considered to be of childbearing potential if she is post-menarcheal, has not reached a postmenopausal state (≤12 continuous months of amenorrhea with no identified cause other than menopause), and has not undergone surgical sterilization (removal of ovaries and/or uterus). The definition of childbearing potential may be adapted for alignment with local guidelines or requirements. Examples of contraceptive methods with a failure rate of ≤1% per year include bilateral tubal ligation, male sterilization, hormonal contraceptives that inhibit ovulation, hormone-releasing intrauterine devices, and copper intrauterine devices. The reliability of sexual abstinence should be evaluated in relation to the duration of the clinical trial and the preferred and usual lifestyle of the patient. Periodic abstinence (e.g., calendar, ovulation, symptothermal, or post-ovulation methods) and withdrawal are not acceptable methods of contraception
10. For women of childbearing potential, a negative serum pregnancy test result during screening period. Women who are considered not to be of childbearing potential are not required to have a pregnancy test.

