5.6.2 Contraception

The study agents may have adverse effects on a fetus in utero. Furthermore, it is not known if the study agents have transient adverse effects on the composition of sperm.

Women of childbearing potential must agree to remain abstinent (refrain from heterosexual intercourse) or use contraceptive methods that result in a failure rate of < 1% per year during the treatment period and for at least 12 months after the last dose of study treatment. Women must refrain from donating eggs during this same period. A woman is considered to be of childbearing potential if she is post-menarcheal, has not reached a postmenopausal state (≥ 12 continuous months of amenorrhea with no identified cause other than menopause), and has not undergone surgical sterilization (removal of ovaries and/or uterus). The definition of childbearing potential may be adapted for alignment with local guidelines or requirements. Examples of contraceptive methods with a failure rate of < 1% per year include bilateral tubal ligation, male sterilization, hormonal contraceptives that inhibit ovulation, hormone-releasing intrauterine devices, and copper intrauterine devices.

The reliability of sexual abstinence should be evaluated in relation to the duration of the clinical trial and the preferred and usual lifestyle of the patient. Periodic abstinence (e.g., calendar, ovulation, symptothermal, or post-ovulation methods) and withdrawal are not acceptable methods of contraception.

Men must agree to remain abstinent (refrain from heterosexual intercourse) or use a condom, and agree to refrain from donating sperm, as defined below: With female partners of childbearing potential or pregnant female partners, men must remain abstinent or use a condom during the treatment period and for at least 5 months after the last dose of polatuzumab vedotin. Men must refrain from donating sperm during this same period.

The reliability of sexual abstinence should be evaluated in relation to the duration of the clinical trial and the preferred and usual lifestyle of the patient. Periodic abstinence (e.g., calendar, ovulation, symptothermal, or postovulation methods) and withdrawal are not acceptable methods of preventing drug exposure. Male patients considering preservation of fertility should bank sperm before study treatment.

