Subjects should be informed that taking the study medication may involve unknown risks to the fetus (unborn baby) if pregnancy were to occur during the study. In order to participate in the study they must adhere to the contraception requirement (described above) for the duration of the study and during the follow-up period defined in section 7.2.2-Reporting of Pregnancy and Lactation to Genentech. If there is any question that a subject will not reliably comply with the requirements for contraception, that subject should not be entered into the study.

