- b. Examples of self-care activities of daily living include bathing, dressing and undressing, feeding oneself, using the toilet, and taking medications, as performed by patients who are not bedridden.
- c. If an event is assessed as a "significant medical event," it must be reported as a serious adverse event
- d. Grade 4 and 5 events must be reported as serious adverse events

f. Pregnancy

If a female subject becomes pregnant while receiving the study drug or within 90 days after the last dose of mosunetuzumab or polatuzumab (within 18 months after the last dose of obinutuzumab), or if the female partner of a male study subject becomes pregnant while the study subject is receiving the study drug or within 90 days after the last dose of mosunetuzumab/polatuzumab (or within 180 days after the last dose of obinutuzumab), a report should be completed and expeditiously submitted to Genentech, Inc. Follow-up to obtain the outcome of the pregnancy should also occur. Abortion, whether accidental, therapeutic, or spontaneous, should always be classified as serious, and expeditiously reported as an SAE. Similarly, any congenital anomaly/birth defect in a child born to a female subject exposed to the study drug should be reported as an SAE.

g. Post-Study Adverse Events

The investigator should expeditiously report any SAE occurring after a subject has completed or discontinued study participation if attributed to prior study drug exposure. If the investigator should become aware of the development of cancer or a congenital anomaly in a subsequently conceived offspring of a female subject (including pregnancy occurring in the partner of a male study subject) who participated in the study, this should be reported as an SAE adequately to Genentech drug Safety during follow up period.

h. Case Transmission Verification of Single Case Reports

The Sponsor agrees to conduct the Case Transmission verification to ensure that all single case reports have been adequately received by Genentech via the investigator emailing Genentech a Quarterly line-listing documenting single case reports sent by the investigator to Genentech in the preceding time period.

The periodic line-listing will be exchanged within seven (7) calendar days of the end of the agreed time period. Confirmation of receipt should be received within the time period mutually agreed upon.

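### Inclusion item 9 asks women for 3 or 6 months of contraception after treatment, with no interval for polatuzumab vedotin, while Section 5.6.2 asks for at least 12 months

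*Combined protocol and SAP*

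**What the plan says.** Section 5.1, inclusion item 9, has women of childbearing potential agree to abstinence or effective contraception during treatment and then "for at least 3 months after the last dose mosunetuzumab or 6 months after the last dose of obinutuzumab". Egg donation is barred over the same period. Polatuzumab vedotin is not mentioned.

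Section 5.6.2 addresses the same women, in largely the same words, but sets the period as "for at least 12 months after the last dose of study treatment", again with egg donation barred throughout. It goes on: "In order to participate in the study they must adhere to the contraception requirement (described above) for the duration of the study". It then adds "during the follow-up period defined in section 7.2.2-Reporting of Pregnancy and Lactation to Genentech".

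For men, Section 5.6.2 does tie a period to the third drug: "for at least 5 months after the last dose of polatuzumab vedotin". Item 11 in Section 5.1 also gives men 5 months, counted from the last treatment.

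The two sections also define the postmenopausal state differently. Item 9 has "has not reached a postmenopausal state (≤12 continuous months of amenorrhea with no identified cause other than menopause"; Section 5.6.2 has "has not reached a postmenopausal state (≥ 12 continuous months of amenorrhea with no identified cause other than menopause".

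**The concern.** Item 9 is the undertaking a woman gives to enter the trial. If a site works from the eligibility list, she can satisfy item 9 in full and still break the rule that Section 5.6.2 makes a condition of taking part. Nothing in the protocol says which section governs. Section 5.6.2 itself warns that the study agents may harm a fetus, so this is a participant-safety instruction on which sites need a single number.

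The silence on polatuzumab vedotin adds to this. The men's rule in Section 5.6.2 shows that the protocol considers an interval after that drug necessary, and Part B delivers it in up to six cycles. Under item 9, a woman in Part B is covered after her last polatuzumab vedotin dose only through the interval attached to obinutuzumab.

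**Working it through.** There is no sample size, power or event count to reproduce. The check sets the two sections side by side and takes differences.

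**Inputs**

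- Item 9 (Section 5.1): 3 months after mosunetuzumab; 6 months after obinutuzumab; nothing for polatuzumab vedotin.
- Section 5.6.2: 12 months after the last dose of any study treatment.
- Section 5.3: Part A is mosunetuzumab alone, through cycle 8. Part B (Table 3) gives obinutuzumab and polatuzumab vedotin together on day 1 of each cycle, ending at cycle 14 day 1.

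**Formula.** When both clocks start at the same dose, shortfall = 12 months − the item 9 interval. For a Part B patient the obinutuzumab interval is used, since that is the later-given of the two drugs that item 9 names.

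| Treatment path | Item 9 minimum | Section 5.6.2 minimum | Shortfall |
|---|---|---|---|
| Part A only | 3 months | 12 months | 12 − 3 = 9 months |
| Part B, both drugs end at cycle 14 day 1 | 6 months | 12 months | 12 − 6 = 6 months |

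The egg-donation ban runs over the same period in each section, so its shortfalls are identical.

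**Could other text settle the conflict?** Section 7.2.1, item f, gives drug-specific windows for female subjects: "within 90 days after the last dose of mosunetuzumab or polatuzumab (within 18 months after the last dose of obinutuzumab". These say when a pregnancy must be reported, not how long contraception must last, so they support neither figure. Section 5.6.2 also points to a section 7.2.2, but no section with that number appears in the available text, so the pointer cannot be used to choose between the two periods.

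**Could a misread character explain it?** Not the durations: no faulty sign turns 3 or 6 months into 12. It could explain the amenorrhea sign. Item 9 contains three inequality signs (the contraceptive failure rate twice, the amenorrhea threshold once) and all three differ from their counterparts in Section 5.6.2. Appendix 14.8 shows a garbled sign before the 40 mL/min creatinine clearance limit.

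**The case against.** The best reply is that the sections do not strictly collide. Each states a minimum, 12 months satisfies both, and Section 5.6.2 binds every participant. Read as a whole, the protocol already demands 12 months, and a woman who stops at 3 or 6 is ignoring Section 5.6.2 rather than following a permission. This is right as far as it goes, and it is why the shortfalls above describe reliance on item 9 alone, not what the whole protocol allows. It does not remove the need for an edit: two different minimums for the same women invite reliance on the shorter one, and item 9 is where eligibility is checked.

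It can also be said that Section 5.6.2 has no formal precedence. That stands. Section 5.1 opens by making its own list a condition of eligibility, so both sections are conditions of taking part. The case for 12 months is that it meets both and covers every drug, not that one section outranks the other. Whether 12 months is pharmacologically the right figure depends on labelling and the investigator brochure, which cannot be consulted here.

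Two stronger readings are tempting, and the documents support neither.

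- A reader might infer that item 9 has its amenorrhea sign reversed, so that recently amenorrheic women escape contraception and, through item 10, the pregnancy test. A misread character is plausible. Even if the sign is printed that way, the parenthesis can be taken as explaining who has *not* reached menopause. On that reading it departs from Section 5.6.2 only at exactly 12 months, on the cautious side. Item 9 also allows local adaptation of the definition, and exclusion 21 bars pregnancy.
- A reader might infer a shortfall of up to about 9.4 months in Part B. That assumes obinutuzumab stops at cycle 9 day 1 while polatuzumab vedotin continues alone to cycle 14 day 1, 5 × 21 = 105 days later. Six months is 182.6 days, leaving 182.6 − 105 = 78 days (2.6 months) of cover, about 9.4 months short of 12. Table 5 permits continuing polatuzumab vedotin alone, for example after anaphylaxis attributed to obinutuzumab, but the timing is assumed and should not be the headline figure.

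**Conclusion.** The duration mismatch is established from the current text. Item 9 falls short of Section 5.6.2 by 9 months for a woman treated in Part A only, and by 6 months for a Part B patient whose two drugs both end at cycle 14 day 1. It sets no interval at all for polatuzumab vedotin. The figures assume that a woman follows item 9 alone and, in Part B, that both drugs run to the last planned dose. How many women would be affected is not stated, and what they are told in the consent form cannot be checked here.

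The amenorrhea sign is a query for the source document, not a finding. The whole point is a correction to a safety instruction; the complete-response endpoint, the planned 42 patients and every operating figure in Section 8.0 are untouched.

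**What to change.** In item 9, replace the two drug-specific intervals with the Section 5.6.2 period, "for at least 12 months after the last dose of study treatment", for both contraception and egg donation. If the sponsor would rather use drug-specific intervals drawn from labelling, put the same intervals in item 9 and Section 5.6.2 and include one for polatuzumab vedotin.

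Optionally, check the printed sign before the 12 months of amenorrhea in item 9. If it is as shown here, align it with Section 5.6.2.

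The cost is one phrase, plus one symbol if the check confirms it. Women face a longer period than item 9 now states, by 9 or 6 months on the two paths above, but no longer than Section 5.6.2 already requires. Nothing changes in sample size, endpoints or analysis.

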5.2 Subject Exclusion Criteria

The subject must be excluded from participating in the trial if the subject:

1. Contraindication to any of the individual components of this regimen or history of severe allergic or anaphylactic reactions to humanized or murine monoclonal antibodies, or known sensitivity or allergy to murine products
2. Prior systemic treatment for lymphoma with the exception of corticosteroids as outlined below. Prior radiotherapy is allowed provided that this site is not used as a measurable site to assess response.
3. Absolute lymphocyte count > 5000/ μ L.
4. History of autoimmune disease, including but not limited to myocarditis, pneumonitis, myasthenia gravis, myositis, autoimmune hepatitis, systemic lupus erythematosus, rheumatoid arthritis, inflammatory bowel disease, vascular thrombosis associated with antiphospholipid syndrome, Wegener's granulomatosis, Sjögren's syndrome, Guillain-Barré syndrome, multiple sclerosis, vasculitis, or glomerulonephritis
 - Patients with a remote history of, or well-controlled autoimmune disease, may be eligible to enroll after discussion with and confirmation by the principal investigator. Patients with controlled Type 1 diabetes mellitus who are on an insulin regimen are eligible for the study.
 - Patients with a history of autoimmune-related hypothyroidism on a stable dose of thyroid replacement hormone may be eligible for this study.
 - Patients with a history of disease-related immune thrombocytopenic purpura or autoimmune hemolytic anemia may be eligible for this study.
 - Patients with eczema, psoriasis, lichen simplex chronicus, or vitiligo with dermatologic manifestations only (e.g., patients with psoriatic arthritis are excluded) are eligible for the study provided all of following conditions are met:
 - i. Rash must cover < 10% of body surface area. Disease is well controlled at baseline and requires only low-potency topical corticosteroids. No occurrence of acute exacerbations of the underlying condition requiring psoralen plus ultraviolet A radiation, methotrexate, retinoids, biologic agents, oral calcineurin inhibitors, or high potency or oral corticosteroids within the previous 12 months.
5. Prior solid organ transplantation
6. Current Grade >1 peripheral neuropathy by clinical examination or demyelinating form of Charcot-Marie-Tooth disease
7. Prior use of any monoclonal antibody within 3 months of the start of Cycle 1; any investigational therapy within 28 days prior to the start of Cycle 1; vaccination with live vaccines within 28 days prior the start of Cycle 1
8. Prior corticosteroid use for conditions related or unrelated to lymphoma are allowed provided that at least 14 days have lapsed since last dose and initiation of study therapy, except for patients who require corticosteroid pre-medication for IV contrast administration.
9. History of other malignancy that could affect compliance with the protocol or interpretation of results except with permission of the principal investigator. The following are eligible without a specific waiver:

- Patients with a history of curatively treated basal or squamous cell carcinoma or melanoma of the skin or in situ carcinoma of the cervix at any time prior to the study are eligible.
 - Patients with any malignancy appropriately treated with curative intent and the malignancy has been in remission without treatment for ≥ 2 years prior to enrollment are eligible.
 - Patients with low-grade, early-stage prostate cancer (Gleason score 6 or below, Stage 1 or 2) with no requirement for therapy at any time prior to study are eligible
10. Evidence of significant, uncontrolled, concomitant diseases that could affect compliance with the protocol or interpretation of results, including significant cardiovascular disease (such as New York Heart Association Class III or IV cardiac disease, myocardial infarction within the last 6 months, unstable arrhythmias, or unstable angina) or pulmonary disease (including obstructive pulmonary disease and history of bronchospasm).
 11. Recent major surgery (within 4 weeks prior to the start of Cycle 1), other than for diagnosis
 12. History or presence of an abnormal ECG that is clinically significant in the investigator's opinion.
 13. Known active bacterial, viral, fungal, mycobacterial, parasitic, or other infection (excluding fungal infections of nail beds) which requires systemic treatment. Patients may proceed with screening during treatment for infection, but systemic treatment must be completed by cycle 1 day 1.
 14. Positive test results for chronic hepatitis B infection (defined as positive hepatitis B surface antigen (HBsAg) serology):
 - Patients with occult or prior hepatitis B infection (defined as positive total hepatitis B core antibody and negative HBsAg) may be included if hepatitis B virus (HBV) DNA is undetectable at the time of screening. These patients must be willing to undergo monthly DNA testing and appropriate antiviral therapy as indicated by institutional standard
 15. Positive test results for hepatitis C (hepatitis C virus (HCV) antibody serology testing)
 - Patients positive for HCV antibody are eligible only if polymerase chain reaction (PCR) is negative for HCV RNA.
 16. History of uncontrolled HIV
 - Patients with known diagnosis of HIV must have undetectable viral load and be on anti-retroviral therapy
 17. Patients with a history of progressive multifocal leukoencephalopathy
 18. History of known central nervous system involvement
 19. History of chronic active EBV
 20. History of hemophagocytic lymphohistiocytosis (HLH) or macrophage activation syndrome (MAS).
 21. Pregnancy or lactation or intending to become pregnant during study

5.3 Study Treatments

For the purposes of this protocol, Part A will refer to the subcutaneous (SC) mosunetuzumab monotherapy portion, while part B will refer to the polatuzumab vedotin and obinutuzumab combination portion.

Part A

The dosing of SC mosunetuzumab is listed in Table 2. Cycle length is 21 days. The rationale for this dosing is described in section 4.2.1. A step-up regimen will be employed to minimize the risk of CRS. Subjects will receive lower doses of the drug on cycle 1 day 1 and achieving the full dose on cycle 1 day 8. The full dose alone will be given on cycle 2 through 8 on day 1 only.

Table 2: SC mosunetuzumab dosing

	Cycle 1			Cycle 2-8
	Day 1	Day 8	Day 15	Day 1
Mosunetuzumab dose (SC)	5 mg	45 mg	45 mg	45 mg

Cycle length = 21 days

Subcutaneous mosunetuzumab will be prepared and administered according to appendix 14.15. Corticosteroids (dexamethasone 10 mg PO or equivalent) should be given pre-dose as well as 24 hours (+/- 4 hours) and 48 hours (+/- 4 hours) post dose during cycles 1 and 2. Oral acetaminophen (500-1000 mg) and/or diphenhydramine (25-50 mg) may also be administered per standard institutional practice prior to mosunetuzumab. Pre-medications from cycle 3 onward are optional provided that the patient did not have cytokine release syndrome during the previous cycle. Hydration and tumor lysis syndrome (TLS) prophylaxis is also at the discretion of the investigator. Corticosteroid administration in cycle 3 and beyond is up to the investigator. However, if a subject experiences CRS then corticosteroids should be administered for the subsequent doses until no CRS is observed.

For SC administration, mosunetuzumab will be administered by qualified staff over 30 seconds to 2 minutes. Refer to appendix 14.15 for more details including syringe size and preferred injection site. The recommended management of injection-site reactions is detailed in Appendix 14.14

Following each mosunetuzumab dose, patients will be observed at least 30 minutes for cycle 1 day 1 for fever, chills, rigors, hypotension, nausea, or other signs and symptoms of CRS. If tolerated during C1D1, subsequent observation times can be reduced to 15 minutes.

Subjects who must permanently discontinue mosunetuzumab monotherapy due to toxicity should have a response assessment with positron emission tomography (PET)/CT as soon as is clinically feasible and be evaluated for consideration of treatment in Part B as outlined below. These subjects would then be realigned to cycle 9 day 1 provided at least 21 days \pm 2 days have passed since the last mosunetuzumab injection

Subjects will undergo a computed tomography (CT) between cycle 4 day 1 and cycle 5 day 1. Those with at least stable disease (SD) or better by Lugano²³ criteria will proceed with treatment for cycles 5-8. Subjects with progressive disease (PD) at this timepoint may proceed with cycles 5-8 if the investigator assesses that the subject is deriving clinical benefit from the study medication (e.g. pseudoprogression). If there is no clinical benefit to this medication seen in patients with PD, subjects should receive additional therapy outside of the protocol.

Imaging with a PET/CT will be performed between cycle 8 day 1 and cycle 9 day 1. Subjects in a complete remission (CR) will not receive any further study therapy and will be observed in long term follow up. For this response assessment, a Deauville score will be assigned by the clinical radiology read. If the sub-investigator or principal investigator disagrees with the Deauville score assigned, another nuclear medicine physician will adjudicate the results.

All other subjects who do not achieve a CR may proceed with Part B of study treatment. Those with progressive disease (PD) may proceed with Part B only if they are deriving clinical benefit from the treatment (e.g., pseudoprogression, mixed response overall reduction in tumor) after discussion with the Principal Investigator.

Mosunetuzumab Dose Modifications/Toxicity Management

Administration of mosunetuzumab will be performed in a clinical setting with immediate access to a code team staff who are trained to monitor for and respond to medical emergencies. Additional management may take place after transfer to the University of Washington Medical Center, where there is access to neurology and nephrology consultation services in the event of cytokine release syndrome and tumor lysis syndrome, respectively.

The recommended management of CRS is listed in Appendix 14.5 and recommended management of hemophagocytic lymphohistiocytosis (HLH) is listed in Appendix 14.6. Details and recommended management of tumor lysis syndrome are listed in section 14.7 and 14.8.

Because TLS (Appendix 14.7 and 14.8) represents a pharmacodynamic effect of mosunetuzumab anti-tumor activity that may result in clinical benefit, patients who experience Grade 4 TLS may be considered for continued study treatment. In order to be considered for subsequent study treatment, all toxicities and laboratory abnormalities

related to TLS resolved within 2 weeks. The decision to continue study treatment should only be made after consultation with the study investigator and approval by the Principal Investigator. Any exceptions must have the approval of the principal investigator.

Patients who experience a treatment-related grade 3 non-hematologic adverse event or serious adverse event not mentioned above will be allowed to delay mosunetuzumab dosing for up to 2 weeks in order to recover from the toxicity. Additional delays must be discussed with the principal investigator prior to considerations of resuming study therapy.

In general, patients receiving mosunetuzumab who experience a Grade 4 non-hematological treatment-related adverse event should discontinue all study treatment and may not be re-treated. Subjects who discontinue mosunetuzumab due to toxicity may proceed to Part B at investigator discretion, but should have a repeat response assessment prior to initiating therapy in Part B.

For those non-hematologic adverse events that are not considered by the investigator to be attributable to another clearly identifiable cause, (e.g., documented disease progression, concomitant medication, or pre-existing medical condition), and thought to be attributable to mosunetuzumab, patients may continue to receive additional doses of mosunetuzumab, provided that the toxicity has resolved to Grade ≤ 1 . Corticosteroids may be used as indicated for the management of non-CRS adverse events related to mosunetuzumab. One can consider resuming mosunetuzumab after resolution of the toxicity to Grade ≤ 1 and steroid dosing of prednisone ≤ 10 mg PO daily or less

- For decreased lab values, the abnormality should have resolved to the lower limit of Grade ≤ 1 , or return to $\geq 80\%$ of the baseline value, whichever is lower.
- For neutropenia, the ANC should resolve to Grade ≤ 2 or return to $\geq 80\%$ of the baseline value, whichever is lower.
- For increased lab values the abnormality should have resolved to the upper limit of Grade ≤ 1 , or return to $\leq 120\%$ of the baseline value, whichever is higher.

In the event that a patient has a toxicity in Cycle 1 necessitating mosunetuzumab interruption for >7 days, the Principal Investigator should be notified and the patient may be required to repeat mosunetuzumab at the highest dose previously tolerated prior to resuming the planned treatment schedule.

If scheduled dosing coincides with a holiday that precludes dosing, dosing should commence on the nearest following date, with subsequent dosing continuing on a 21-day schedule as applicable.

Patients who discontinue all study treatment for adverse events should continue to have disease assessments per institutional standard of care.

Additional guidance on the management of other risks that may be associated with mosunetuzumab is described in Appendix 14.9 (Neurologic AEs), Appendix 14.10 (Tumor Inflammation or flare), Appendix 14.11 (Neutropenia and thrombocytopenia), Appendix 14.12 (Infections) and Appendix 14.13 (Elevated Liver Enzymes).

Part B

For patients eligible for treatment in Part B, treatment will commence with cycle 9 day 1. This may be delayed for patients who require a washout of an agent listed in appendix 14.4. Cycle length is 21 days. Polatuzumab vedotin will be administered on day 1 of each cycle. Obinutuzumab 1000 mg will be administered (See table 5 and 6 for details on pre-medications and infusion related reaction management) on cycle 9 day 1, day 8, and day 15. From cycle 10 onwards obinutuzumab will only be administered on day 1 (1000 mg). Part B will be administered for 6 total cycles (through cycle 14). A response assessment by CT should be performed after cycle 11, and an end of treatment PET/CT should be performed after cycle 14. Obinutuzumab should be administered prior to polatuzumab vedotin on days that both drugs are administered.

Table 3: Part B dosing table

	Cycle 9			Cycle 10-14
	Day 1	Day 8	Day 15	Day 1
Obinutuzumab IV	1000 mg	1000 mg	1000 mg	1000 mg
Polatuzumab vedotin IV	1.8 mg/kg			1.8 mg/kg

Cycle length = 21 days

Dose Modification

These guidelines pertain to dose delays and modifications based on physical examination findings, observed toxicities, and laboratory results obtained within 72 hours before study treatment administration. The determination of all dose and schedule modifications will be made on the basis of the investigator's assessment of ongoing clinical benefit with continuing study treatment. Table 4 shows the recommended steps of dose reduction for polatuzumab vedotin based on toxicities in Table 5 and Table 6. In general, obinutuzumab should be given at the fixed doses outlines above, but treatment may be interrupted due to toxicities as outlined in the sections below.

Table 4: Recommended steps of dose reduction for polatuzumab vedotin

Dose Level	Polatuzumab vedotin
Starting dose	1.8 mg/kg per cycle
First dose reduction	1.4 mg/kg per cycle
Second dose reduction	Permanently discontinue drug

Dose of polatuzumab vedotin should not be increased after a reduction unless there has been a change in attribution (no longer attributable to polatuzumab vedotin) of the adverse event that led to the initial reduction.

Treatment Interruptions and Schedule Modification

Refer to the obinutuzumab and polatuzumab vedotin US prescribing information for additional details.

Study treatment may be temporarily suspended in patients who experience toxicity considered to be related to study drug (see Table 4). Aside from the withholding of polatuzumab vedotin for neuropathy per Table 4 and Table 5, study drugs withheld for more than 14 days because of toxicity should be discontinued, unless resumption of treatment is approved following investigator discussion with the principal investigator. Study treatment may be suspended for reasons other than toxicity (e.g., surgical procedures) with principal investigator approval. If scheduled dosing coincides with a holiday that precludes dosing, dosing should commence on the nearest following date, with subsequent dosing continuing on a 21-day schedule as applicable.

Specific guidelines around dosage modifications for Part B are detailed below.

Patients who are receiving study treatment and experience toxicities should undergo dose interruptions and reductions, per instructions in Table 5. All considerations of dose and schedule modifications should be discussed with the principal investigator.

Dose Discontinuation

Dosing delays exceeding 14 days in the initiation of the next planned cycle of treatment will require study treatment discontinuation unless principal investigator approval is obtained to continue on study treatment.

Patients should permanently discontinue polatuzumab vedotin if further dose reduction is indicated beyond 1.4 mg/kg. In this case, subjects may still continue to receive obinutuzumab monotherapy through cycle 14.

If an individual study drug (obinutuzumab or polatuzumab vedotin) is omitted during a cycle for any reason including toxicity while the other drug is administered, the omitted drug will not be made up at a later date.

Patients discontinuing individual agents should remain in the study and continue with all protocol-defined assessments and treatments.

Patients who discontinue all study treatment for adverse events should continue to have disease assessments per institutional standard of care.

GCSF may be administered at the discretion of the investigator for persistent neutropenia resulting in delay of treatment

Tumor Lysis Syndrome

As many patients will have partially treated lymphoma by Cycle 9 day 1, additional tumor lysis syndrome prophylaxis will be at the discretion of the investigator based on most recent imaging and laboratory values.

Table 5: Dose interruptions, reductions, and discontinuations of study agents

Event(s)	Dose delay or modification
Grade 3 or 4 neutropenia on day 1 of cycle 10-14 with or without infection or fever, first delay ^a	
 • Delay all study treatment for a maximum of 14 days. • When ANC recovers to $\geq 1000/\mu\text{L}$, Polatuzumab vedotin dosing should remain t
Recurrent Grade 3 or 4 neutropenia on day 1 of cycle 11-14 with or without infection or fever	
 • Delay all study treatment for a maximum of 14 days. • If ANC recovers to $\geq 1000/\mu\text{L}$ within 7 days of day 1, Resume at same dose. If g required for neutrophil recovery, then next doses of polatuzumab vedotin dosing s GCSF use is at the discretion of the investigator, but recommended for subjects w interruption due to neutropenia.
Thrombocytopenia Grade 3-4	
 • Delay all study treatment for a maximum of 14 days • When platelet count recovers to $\geq 75,000/\mu\text{L}$, treatment may resume. Polatuzuma reduction can be considered in patients with recurrent grade 3-4 thrombocytopenia • If primary cause is due to lymphoma, dose delay or reduction may not be needed
Bilirubin between 1.5 and 3.0 mg/dL	
 • Dose reduction to next lowest dose level should be avoided if hyperbilirubinemia hepatic injury (i.e., hemolysis or Gilbert's disease). In these cases, dose reduction be guided by direct bilirubin levels. In these cases, dose delay considerations shou bilirubin levels and polatuzumab vedotin should be held until direct bilirubin is Gr Obinutuzumab may continue as scheduled. • If the AE severity remains unchanged by the start of the next expected cycle date polatuzumab vedotin and administer obinutuzumab at the recommended dose. The polatuzumab vedotin and will not be made up at a later date. • Doses of polatuzumab vedotin should not be re-escalated for future cycles witho principal investigator. The withheld doses of polatuzumab vedotin and will not be date.
Bilirubin > 3.0 mg/dL	
 • Polatuzumab vedotin dose delay should be avoided if hyperbilirubinemia is not r injury (i.e., hemolysis or Gilbert's disease). In these cases, dose delay consideratio

	
by direct bilirubin levels and polatuzumab vedotin should be held until direct bilirubin levels are ≤ 1.5 mg/dL. Obinutuzumab may continue as scheduled.
 
 • If the AE severity remains unchanged by the start of the next expected cycle date, hold polatuzumab vedotin and administer obinutuzumab at the recommended dose. The withheld doses of polatuzumab vedotin and will not be made up at a later date. • Doses of polatuzumab vedotin should not be re-escalated for future cycles without the approval of the principal investigator. The withheld doses of polatuzumab vedotin and will not be made up at a later date.
Grade 1 neuropathy	
 • No study treatment modification is recommended for Grade 1 sensory or motor peripheral neuropathy.
Grade 2 sensory peripheral neuropathy	
 • Hold Polatuzumab vedotin until improvement to Grade ≤ 1. Continue obinutuzumab as scheduled. • Resume at next lowest dose level when Grade ≤ 1. • If the AE severity remains unchanged by the start of the next expected cycle date, hold polatuzumab vedotin and administer obinutuzumab at the recommended dose. The withheld doses of polatuzumab vedotin and will not be made up at a later date. • Doses of polatuzumab vedotin should not be re-escalated for future cycles without the approval of the principal investigator. The withheld doses of polatuzumab vedotin and will not be made up at a later date.
Grade 3 sensory peripheral neuropathy, or Grade 2 or 3 motor peripheral neuropathy	
 • If the AE severity remains unchanged by the start of the next expected cycle date, hold polatuzumab vedotin and administer obinutuzumab at the recommended dose. The withheld doses of polatuzumab vedotin and will not be made up at a later date. • When the AE improves to Grade ≤ 1 peripheral sensory neuropathy and/or Grade ≤ 2 motor neuropathy, the polatuzumab vedotin can be restarted at a reduced dose.
Grade 4 neuropathy (including peripheral sensory or motor neuropathy)	
 • Discontinue polatuzumab vedotin treatment permanently. • Patients should be evaluated regarding the continuation of obinutuzumab monotherapy based on their risk/benefit.
Grade 3 or 4 constipation or ileus	
 • Polatuzumab vedotin should be held until improvement to Grade ≤ 2. Obinutuzumab should be continued, or delayed at the discretion of the investigator. • Consider reducing polatuzumab vedotin to the next dose level (Table 4) after improvement to Grade ≤ 2.

